8.1.5. Period of Observation and Reporting

All AEs for Cohort 1 with a start date occurring between Visit 3 (Day 1) and through the last subject visit must be recorded on the CRF. All AEs for Cohort 2 with a start date occurring between Visit 2 (Week -4) and through the last subject visit must be recorded on the CRF. During the study, sites should query subjects on the status of any ongoing AEs at subsequent clinic visits. Depending on the reported event, the Investigator may need to follow-up on the status of AEs with the study subject between visits (e.g., phone, text, or email). At the conclusion of the trial, any ongoing AEs will be followed until at least 28 days after the final explantation procedure to determine the final reported outcome of the event.

For SAEs, and pregnancy reports, the active reporting period to the Sponsor begins from the time the subject provides informed consent through and including 28 days after the final explantation of all of the investigational product units.

SAEs and pregnancies occurring after the period of observation has ended should be reported to the Sponsor if the Investigator becomes aware of an event. At a minimum, all SAEs the Investigator assesses as possibly related to the investigational product are to be reported to the Sponsor.

The reporting period for AEs and SAEs may overlap with the timing of the subject's participation in the separate follow-up study. Further details on how to report ongoing AEs spanning the period between this protocol and the separate follow-up study will be outlined in the separate follow-up protocol.

All AE reporting, including SAEs and suspected unexpected serious adverse reactions (SUSARs), will be carried out in accordance with applicable regulations.

8.2. Serious Adverse Events (SAE)

An SAE is any untoward medical occurrence meeting at least one of the following criteria:

- Results in death:
- Is life-threatening (immediate risk of death);
- Requires in-patient hospitalization or prolongation of existing hospitalization;
- Results in persistent or significant disability/incapacity (substantial disruption of the ability to conduct normal life functions);
- Results in congenital anomaly/birth defect;
- Constitutes an Important Medical Event in the opinion of the Investigator and/or Sponsor.

Medical and scientific judgment is exercised in determining whether an event is an important medical event. An important medical event may not be immediately life threatening and/or result in death or hospitalization. However, if it is determined the event may jeopardize the subject or may require intervention to prevent one of the other SAE criteria, the important medical event should be reported as serious.

Based on the definition above, severe hypoglycemic events (SHE) may or may not be reported as SAEs and will be classified at the Investigator's discretion. In all instances, SHEs are to be recorded on the hypoglycemic event (HE) CRF.

AEs resulting in hospitalization or prolongation of a hospitalization are considered serious. Any formal admission (even if less than 24 hours) to a healthcare facility meets these criteria. Admission also includes transfer within the hospital to an acute or intensive care unit (e.g., from the psychiatric wing to a medical floor, medical floor to a coronary care unit, neurological floor to a tuberculosis unit).

Hospitalization does not include the following:

• Rehabilitation facilities;

- Hospice facilities;
- Respite care (e.g., caregiver relief);
- Skilled nursing facilities;
- Nursing homes;
- Emergency room visits;
- Outpatient surgical procedures.

Hospitalization or prolongation of hospitalization in the absence of a precipitating, clinical AE is not in itself an SAE. Examples include:

- Admission for treatment of a pre-existing condition not associated with the development of a new AE or with a worsening of the preexisting condition (e.g., for work-up of persistent pre-treatment lab abnormality);
- Social admission (e.g., subject has no place to sleep);
- Administrative admission (e.g., for yearly physical exam);
- Protocol-specified admission during a study (e.g., for a procedure required by the study protocol);
- Optional admission not associated with a precipitating clinical AE (e.g., for elective cosmetic surgery);
- Hospitalization for observation without a medical AE;
- Pre-planned treatments or surgical procedures should be noted in the baseline medical history assessment and documentation for an individual subject.

Diagnostic and therapeutic non-invasive and invasive procedures, such as surgery, should not be reported as AEs. However, the medical condition for which the procedure was performed should be reported if it meets the definition of an AE. For example, an acute appendicitis that begins during the AE reporting period should be reported as the AE, and the resulting appendectomy should be recorded as treatment of the AE.

8.2.1. Suspected, Unexpected Serious Adverse Reactions (SUSAR)

A SUSAR is a serious adverse reaction which is thought to be causally related to the investigational product, surgical procedure, and/or immunosuppression regimen and which is unexpected to occur. Reporting of SUSARs to the Sponsor, all participating Investigators, the Ethics Committee, and to the Regulatory Authorities is mandatory in accordance with applicable regulations.

Because of the limited shelf-life of the investigational product, the results of the 14-day sterility testing of VC-01 are not available until after implantation occurs. In the unexpected event of positive culture results from this test, the Sponsor will notify the Investigator, who will then notify the subject. The Sponsor will initiate further testing of the positive sample to identify the microorganism and conduct a root-cause analysis. The Investigator and Sponsor will evaluate any additional actions required to appropriately monitor the subject based on the results of the sample.

If the medical condition of the patient is impacted as a consequence of the microorganism causing the positive sterility results, the event should be reported as a SUSAR.

8.2.2. SAE Reporting Procedures

If an SAE occurs, the Sponsor must be notified using the Sponsor's SAE Reporting Form within 24 hours of the Investigator becoming aware of the occurrence of the event. In particular, if the SAE is fatal or life-threatening, notification to the Sponsor must be made immediately, irrespective of the extent of available AE information. This timeframe also applies to additional, new information (follow-up) on previously reported SAE reports as well as to the initial and follow-up reporting on cases of exposure during pregnancy and exposure via breastfeeding using the Sponsor's Pregnancy Report Forms.

In the rare event the Investigator does not become aware of the occurrence of an SAE immediately (e.g., a study subject initially seeks treatment elsewhere), the Investigator is to report the event within 24 hours after learning of it and document the date and time of awareness of the AE.

For all SAEs, the Investigator is obligated to pursue and provide information to the Sponsor in accordance with the timeframes for reporting specified above. In addition, an Investigator may be requested by the Sponsor to obtain specific, additional, follow-up information in an expedited fashion. The information collected for SAEs is more detailed than that captured on the AE CRF. In general, this will include a description of the SAE in sufficient detail to allow for a complete medical assessment of the case and independent determination of possible causality. Information on other possible causes of the event, such as concomitant medications and illnesses must be provided. In the event of a subject death, a summary of available autopsy findings must be submitted as soon as possible to the Sponsor.

8.3. Hypoglycemic Events

In Cohort 1, all hypoglycemic events occurring during study participation are expected to be unrelated to the investigational product. The number of sentinel units implanted in subjects enrolled into this study results in a sub-therapeutic dose. Additionally, multiple sentinels will be explanted prior to the units reaching the potential for functional engraftment. Therefore, the amount of endogenous insulin released from implanted VC-01 units is expected to have no effect on glycemic control.

Therefore, since hypoglycemia is a symptom of the disease under study, routine hypoglycemic events will not be captured as adverse events in Cohort 1.

However, throughout Cohort 2, hypoglycemic events and severe hypoglycemic events (SHE) will be captured as described in **Section 7.16**.

8.4. Reporting of Pregnancy

For investigational products, an exposure during pregnancy (also referred to as Exposure in Utero [EIU]) occurs if an enrolled female subject becomes, or is found to be, pregnant while in the study.

Pregnancy itself is not an AE. However, adverse consequences of pregnancy should be reported as an AE or SAE as applicable.

If the subject (or subject's partner) becomes or is found to be pregnant during the study, the Investigator must submit this information to the Sponsor on a Pregnancy Report Form. This must be done within 24 hours of awareness of the event. The information submitted should include the anticipated date of delivery (if known). See below for information related to termination of pregnancy. All confirmed EIU cases and follow-up information will be recorded in a Pregnancy Safety Database.

Follow-up is conducted to obtain pregnancy outcome information for all pregnancy reports. The Investigator will follow the pregnancy until completion (or until pregnancy termination) and notify the Sponsor of the outcome as a follow-up to the initial Pregnancy Report Form. In the case of a live birth, the structural integrity of the neonate can be assessed at the time of birth. In the event of a termination, the reason(s) for termination should be specified, and, if clinically possible, the structural integrity of the terminated fetus should be assessed by gross visual inspection (unless pre-procedure test findings are conclusive for a congenital anomaly and the findings are reported).

If the outcome of the pregnancy meets the criteria for an SAE (i.e., ectopic pregnancy, spontaneous abortion, intrauterine fetal demise, neonatal death, or congenital anomaly [in a live born, a terminated fetus, an intrauterine fetal demise, or a neonatal death]), the Investigator should follow the procedures for reporting SAEs.

Additional information about pregnancy outcomes that are reported as SAEs include:

- Spontaneous abortion includes miscarriage and missed abortion;
- Neonatal deaths that occur within one month of birth should be reported, without regard to causality, as SAEs.
- Death of an infant older than one month should be reported as an SAE if the Investigator assesses the infant death as related or possibly related to exposure to investigational product.

Additional information regarding the exposure during pregnancy may be requested by the Investigator. Further follow-up of birth outcomes will be handled on a case-by-case basis (e.g., follow-up on preterm infants to identify developmental delays).

8.5. Data Safety Monitoring Board (DSMB)

An independent Data Safety Monitoring Board (DSMB) is available to meet throughout the study to review accumulated data at the request of the Sponsor. There are no required DSMB meetings specific to the administration of this trial during Cohort 1. Any DSMB meetings conducted during Cohort 1 will be performed on an ad hoc basis. During Cohort 2, it is anticipated that the DSMB will meet on a regular basis to review accumulating data from the study.

The DSMB will consist of at least 3 members, including a statistician. No Investigator involved in the trial or anyone connected to the Sponsor or participating vendors such as a CRO may be a member of the DSMB. Based on the review of the study data, the DSMB may make recommendations regarding the conduct of the study. These may include, but are not limited to, amending safety monitoring procedures, modifying the protocol or consent, terminating the study, or continuing the study as designed. The discussions and decisions of the DSMB will be summarized in written minutes and provided to the Sponsor. When necessary, summary DSMB

minutes may be distributed to participating sites for submission to Ethics Committees. A separate DSMB Charter will direct the activities of the Board.

The approximate timing of DSMB meetings are noted below:

- Cohort 1: Any DSMB meetings conducted during Cohort 1 will be on an ad hoc basis. After a minimum of three (3) subjects from Cohort 1 have reached the Week 4 clinic visit and the data are available, the Sponsor may request that the DSMB meet to review the accumulated data.
- Cohort 2: Once Cohort 2 begins enrollment, the DSMB will meet every three (3) to six (6) months, until the last visit of the last Cohort 2 subject has occurred.

Additional meetings of the DSMB may be scheduled based on data review needs or by request by the Sponsor or the DSMB.

8.6. Study Stopping Rules

If any of the following safety events are noted to occur in the study, an ad-hoc meeting of the DSMB will be requested. The DSMB will review the data and can recommend stopping the study for any of the following:

- 1. Two or more subjects have pronounced immune responses to VC-01.
- 2. Two or more subjects experiencing an NCI-CTCAE Grade 3 (severe) treatment emergent adverse event (TEAE) in the same Medical Dictionary for Regulatory Activities (MedDRA) system organ class (SOC) and preferred term (PT) considered to be possibly or probably related to the investigational product. TEAE is defined as an AE that starts on or after the date of implant surgery.
- 3. After a minimum of eight weeks post-implantation, there are two or more subjects who each experience two or more Severe Hypoglycemic Events (SHE) over a 6-month period unrelated to anything other than VC-01. This assumes the SHE occurred despite reasonable adjustments in the exogenous insulin requirements and appropriate dietary adjustments.
- 4. Two or more subjects develop SAEs deemed related to the implantation of VC-01 itself; examples of such events are noted below:
 - a. Development of an off-target cell growth (i.e., teratoma) within the unit which is noted on ultrasound and confirmed by pathologist.
 - b. A related, severe, persistent, inflammatory response that does not resolve (e.g., severe site reactions, urticaria, erythematous rash, anaphylaxis, acute respiratory insufficiency, swelling).
- 5. Two or more subjects have an unexplained graft malfunction requiring explant.

In addition to these events, the DSMB can consider recommending a temporary delay or hold on enrollment in the trial for events considered by the Investigator to be related to VC-01. The DSMB can also recommend treatment continue for a shorter duration (i.e., less than the planned 6 months (Cohort 1) or 12 months (Cohort 2)) or with a fewer number of implanted units. The DSMB can also recommend the Sponsor close the study at any time in response to any legitimate safety

concerns. The Sponsor will communicate DSMB recommendations to each site in a timely fashion. Each site's Ethics Committee will make the ultimate decision to delay enrollment, modify treatment duration, or stop the study based on DSMB recommendations.

The Sponsor may also decide to terminate the study for other safety or lack of efficacy reasons. In the event the study is terminated, all subjects will have their VC-01 units explanted, and all subjects will be monitored post-explant in the separate follow-up safety study.

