8.1. Adverse Events

An adverse event (AE) is any untoward medical occurrence in a clinical investigation subject administered a product or medical device. Adverse events need not necessarily have a causal relationship with the treatment or usage.

Examples of AEs include, but are not limited to:

- Abnormal test findings;
- Clinically significant symptoms and signs (changes from baseline status);
- Clinically significant changes in physical examination findings;
- Hypersensitivity;
- Sensitization to the line;
- Progression/worsening of underlying disease (includes worsening diabetes)

All observed or volunteered AEs regardless of suspected causal relationship to the investigational product will be reported as described in the following sections. Non-clinically significant physical exam observations will not be reported as an AE.

For all AEs, the Investigator must pursue and obtain information adequate both to determine the outcome of the AE and to assess whether it meets the criteria for classification as a serious adverse event (SAE) requiring immediate notification to the Sponsor and the Ethics Committee. For all AEs, sufficient information should be obtained by the Investigator to determine the causality of the AE. The Investigator is required to assess causality. Follow-up by the Investigator may be required until the event or its sequelae resolve or stabilize at a level acceptable to the Investigator, and the Sponsor concurs with that assessment.

As part of ongoing safety reviews conducted by the Sponsor, any non-serious AE that is determined by the Sponsor to be serious will be reported by the Sponsor as a SAE. To assist in the determination of case seriousness, further information may be requested from the Investigator to provide clarity and understanding of the event in the context of the clinical trial.

As required on the AE CRFs, the Investigator will use the National Cancer Institute Common Terminology Criteria for Adverse Event (NCI-CTCAE) guidelines to describe the maximum intensity of the AE. For purposes of consistency, these intensity grades are defined as follows:

| MILD | Asymptomatic, or mild symptoms, clinical or diagnostic observations noted; intervention not indicated |
|------------------|---|
| MODERATE | Local or noninvasive intervention indicated |
| SEVERE | Medically significant but not immediately life threatening, hospitalization or prolonged hospitalization. |

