| LIFE-THREATENING | Life-threatening consequences, urgent intervention indicated |
| DEATH | Death related to AE |

Note the distinction between the severity and the seriousness of an AE. A severe event is not necessarily an SAE. For example, a headache may be severe (medically significant) but would not be classified as serious unless it met one of the criteria for SAEs (See Section 8.2).

Likewise, AEs may receive a temporal classification based on the start date of the event relative to when the investigational product was first administered. A treatment emergent AE (TEAE) is defined as an AE that starts on or after the date of implant surgery.

In addition, if the Investigator determines an SAE is associated with study procedures, the Investigator must record this causal relationship in the subject's source documents and CRF, as appropriate, and report such an assessment in accordance with the SAE reporting requirements, if applicable.

It should be noted that the form for collection of SAE information will not be the same as the AE CRF. Where the same data are collected, the forms must be completed in a consistent manner. AEs should be reported using concise medical terminology.

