8.1.1. Causality Assessment of Adverse Events

The Investigator's assessment of causality must be provided for all AEs (serious and non-serious). In relation to implantation with VC-01, there are two (2) main components to assessing causality. The Investigator's causality assessment must include a determination of whether there exists a reasonable possibility that:

- The investigational product (VC-01) itself caused or contributed to the AE.
- The surgical procedure (implantation or explanation) caused or contributed to the AE.

In evaluating the causal relationship of an AE to VC-01 and the surgical procedures, it is possible for the Investigator to determine causality as being associated to one or more of these factors. Conversely, the Investigator can determine that none of these relate to the AE.

If the Investigator's final determination of causality is unknown, and the Investigator does not know if the investigational product, surgical procedure, or immunosuppression drugs caused the event, then the event will be classified as "related to investigational product" for reporting purposes. If the Investigator's causality assessment is "unknown but not related to investigational product", this should be clearly documented on the subject's source records.

Relationship of an AE to VC-01 and the surgical procedures will be assessed as follows:

Not Related: A clinical event including laboratory test abnormalities without a temporal relationship to the investigational product exposure or the surgical procedures which makes a causal relationship improbable, and/or in which other drugs, chemicals, or underlying disease provides plausible explanations.

Unlikely Related: A clinical event including laboratory test abnormalities without any temporal relationship to the investigational product exposure or the surgical procedures which makes a causal relationship doubtful or unlikely and/or in which other drugs, chemicals, or underlying disease provides plausible explanations.

Possibly Related: A clinical event, including laboratory test abnormality, with a reasonable time sequence to exposure of the investigational product or the surgical procedures, but which could also be explained by concurrent disease or other drugs or chemicals.

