Definitely Related: A clinical event, including laboratory test abnormality, with a reasonable time sequence to the investigational product exposure or surgical procedures, unlikely to be attributed to concurrent disease or other drugs or chemicals, and which follows a clinically reasonable response.

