8.1.4. Adverse Events of Special Interest (AESI)

Certain AEs may require additional investigation to ensure appropriate information and data are captured to appropriately evaluate the clinical development of VC-01. These are considered adverse events of special interest (AESI) and may include but are not limited to:

- AEs leading to the unexpected or premature explantation of sentinel or dose-finding (VC-01-DF) units are considered AESI.
- AEs that result in early withdrawal from the study.
- Severe hypoglycemic events occurring after VC-01 implantation possibly or definitely related to VC-01.

If an AESI occurs, the Sponsor may request that additional data be collected for these events.

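### Stopping rule 2 names a causality rating, 'probably', that is not on the protocol's scale and leaves out the top rating, 'Definitely Related'

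*Protocol*

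**What the plan says.** Protocol 8.6 lists five safety events that lead to a request for an ad-hoc DSMB meeting, after which the board can recommend stopping. Rule 2 concerns two or more subjects with a Grade 3 treatment-emergent adverse event in the same MedDRA system organ class and preferred term, "considered to be possibly or probably related to the investigational product".

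Protocol 8.1.1 sets the scale on which investigators rate relatedness to VC-01 and to surgery. It defines four ratings. The lower two are Not Related and Unlikely Related. The upper two begin "Possibly Related: A clinical event, including laboratory test abnormality" and "Definitely Related: A clinical event, including laboratory test abnormality". The same section says that when the "final determination of causality is unknown, and the Investigator does not know if the investigational product", the surgery or immunosuppression was responsible, the event is classed as product-related for reporting.

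Protocol 8.1.4, on adverse events of special interest, describes severe hypoglycemic events as "possibly or definitely related to VC-01", which matches the scale. The SAP (7.3.7.1 and 7.3.7.2) tabulates events by relationship but defines no other scale and does not say where *probably* would fall.

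**The concern.** The rule and the scale share only one rating, *Possibly*. An investigator cannot record *Probably*, and an event recorded as *Definitely* is not one the rule names. Followed to the letter, the trigger fires on weaker evidence of causality and stays silent on the strongest, which is the reverse of what a stopping rule is for.

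At stake is whether a repeated, severe, product-related event prompts a DSMB review automatically or only if someone chooses to ask for one. The product is an implanted stem-cell therapy at an early stage, so the trigger should be readable directly from the rating on the case report form.

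Rule 2 also does not say whether events of unknown causality count, although 8.1.1 treats them as related for reporting.

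**Working it through.** No event rates are given in the documents, so this is a comparison of texts and a count of rating combinations, not a probability calculation.

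**Step 1. Match the rule to the scale.**

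| Rating | On the 8.1.1 scale? | Named in rule 2? | Named in 8.1.4? |
|---|---|---|---|
| Not Related | yes | no | no |
| Unlikely Related | yes | no | no |
| Possibly Related | yes | yes | yes |
| Probably Related | no | yes | no |
| Definitely Related | yes | no | yes |

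The text of 8.1.1 shows no redaction mark or gap where a fifth rating might have been.

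**Step 2. Count the pairs.** Two subjects with related events can have ratings drawn from {Possibly, Definitely}. The unordered pairs number 2 × 3 / 2 = 3.

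| Ratings of the two events | Rule 2 read literally | *Probably* read as *Definitely* |
|---|---|---|
| Possibly, Possibly | triggers | triggers |
| Possibly, Definitely | does not trigger | triggers |
| Definitely, Definitely | does not trigger | triggers |
| Pairs that trigger | 1 of 3 | 3 of 3 |

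**Step 3. Ask what the other rules in 8.6 catch.**

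- Rule 1 ("Two or more subjects have pronounced immune responses to VC-01"), rule 3 (repeated severe hypoglycemia attributable only to VC-01) and rule 5 (unexplained graft malfunction needing explant) require neither seriousness nor a rating from the scale.
- Rule 4 covers related serious events. Under 8.1, "any non-serious AE that is determined by the Sponsor to be serious will be reported by the Sponsor as a SAE", so some events first recorded as non-serious can reach rule 4.
- Rule 4 does not replace rule 2, because 8.1 also states: "A severe event is not necessarily an SAE".

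What is left is a repeated, product-related, non-serious Grade 3 event outside rules 1, 3 and 5. Implant site swelling, reported with VC-01 in Protocol 1.4.2, is one type that might fall there. The documents give no grade or attribution for it.

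**Step 4. Bound the delay.** Under Protocol 8.5, the DSMB meets every 3 to 6 months once Cohort 2 enrols. If that schedule is kept, the wait from a missed trigger to the next scheduled meeting is 0 to 6 months, and shorter if a discretionary meeting is called. Before Cohort 2 enrols no meetings are required. Protocol 1.1 describes device configurations as already tested in Cohort 1, so that period appears to be at least partly past.

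**The case against.** The best reply is that nobody would apply the rule in the harmful way. The scale has only two related ratings, so a phrase naming two levels of relatedness most naturally means both. The definition of Definitely Related in 8.1.1 supports this: it asks that other causes be unlikely, which is close to what *probably related* usually means. On that reading nothing is lost.

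Other safeguards narrow the gap:

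- Rule 4b gives severe site reactions and swelling among its examples, though only as serious events with a persistent response.
- Protocol 7.6 lists severe reactions at more than one implantation site, and swelling, among signs of a possible immunological reaction, and requires immediate contact with the sponsor if one is suspected. This weakens the swelling example: only transient, non-immune, non-serious severe swelling would be left.
- Hospitalization is part of the definition of a severe event in 8.1 and makes an event serious under 8.2, so many Grade 3 events would reach rule 4.
- Protocol 13.6 makes malfunctioning units that cause severe or serious events a withdrawal criterion, but for the individual subject and without a DSMB trigger.
- The DSMB charter, which is not among the documents, may define relatedness (Protocol 10.3.1).

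The meeting schedule in 8.5 is also described as approximate, so 6 months is a planned interval and not a guarantee.

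These points stand, and they limit the size of the problem. They do not remove it. None of the other rules covers repeated non-serious Grade 3 events as such. Under 8.6 a meeting must be requested when a rule is met, whereas the extra meetings in 8.5 are discretionary. The sensible reading has to be supplied by the reader, and 8.1.4 shows that the protocol had the exact words available.

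**Conclusion.** The concern holds. Rule 2 uses a rating that investigators cannot assign and omits the strongest one they can, so the protocol is inconsistent with itself on an operative safety trigger. Read literally, 1 of 3 pairs of related ratings triggers the rule; read as probably intended, all 3 do. This is a count of label combinations and says nothing about how often the gap would matter.

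The consequence is modest. The rule requests a meeting and does not stop the trial by itself. Once Cohort 2 enrols, a missed trigger would delay review by about 6 months at most, assuming the planned meeting interval is kept. The conclusion assumes that 8.1.1 is the scale in use and that the charter does not already resolve the mismatch. The correction should be made, but the trial need not wait for it.

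**What to change.** In rule 2 of Protocol 8.6, replace the relatedness phrase with: *possibly or definitely related to the investigational product, including events of unknown causality classified as related under Section 8.1.1*. If the DSMB charter repeats the rule, use the same words there.

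Optionally, change the grade to *Grade 3 or higher*, so that a non-serious Grade 3 event in one subject and a Grade 4 event of the same preferred term in another count together. This is a separate refinement, and the main correction does not depend on it.

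The cost is one sentence at the next protocol amendment and matching charter text if needed. No procedures, data or analyses are added.
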